APPENDIX H: CONTRACEPTIVE REQUIREMENTS

Effective methods of contraception for use in this study are:

- a. Intrauterine device.
- b. Stable dose of hormonal birth control, such as those listed below, for at least 3 months prior to enrollment.
 - Hormonal contraceptive tablets.
 - Injectable hormonal contraceptives.
 - Implanted hormonal contraceptives.
 - Cutaneous contraceptive patches.
 - Intravaginal hormonal contraceptive rings.
- c. At least 1 barrier method. Effective barrier methods for use in this study are:
 - Male or female condom.
 - Diaphragm.

A female is considered to be of "childbearing potential" if she has experienced menarche and is not permanently sterile or postmenopausal (postmenopausal is defined as 12 consecutive months with no menses without an alternative medical cause and with a serum follicle-stimulating hormone test result in the postmenopausal range). Surgically sterile females (eg, status post-hysterectomy, bilateral oophorectomy, or bilateral tubal ligation) may enter the study with historical documentation of the surgical procedure and a negative pregnancy test at study entry. If a female participant has a male partner who has had surgery to prevent pregnancy (vasectomy), that will be considered evidence of effective contraception for the purpose of this study, provided: a) that the male partner is the sole sexual partner of the participant, and b) historical documentation of the procedure is provided.

In addition to routine contraceptive methods, "effective contraception" also includes heterosexual celibacy for the entire duration of the study and for 90 days after the last dose of study treatment. Abstinence (celibacy) should only be used as a contraceptive method if it is in line with the participant's usual and preferred lifestyle. Periodic abstinence (calendar, symptothermal, postovulation methods) is not an acceptable method of contraception. If at any point a previously celibate participant chooses to become heterosexually active during the time period for use of contraceptive measures specified above, he/she is responsible for initiating effective contraceptive measures as defined above

Signature Page for AVM-003-HC Protocol v5.0 23Feb2022 VV-CLIN-000106 v3.0

Approval Task	
	23-Feb-2022 20:43:43 GMT+0000

Signature Page for AVM-003-HC Protocol v5.0 23Feb2022 VV-CLIN-000106 v3.0

RBC	Red Blood Cell		
SAE	Serious Adverse Event		
SAP	Statistical Analysis Plan		
SDTM	Study Data Tabulation Model		
TEAE	Treatment-Emergent Adverse Event		
TESAE	Treatment-Emergent Serious Adverse Event		
ULN	Upper Limit of Normal		
WHO	World Health Organization		

1 INTRODUCTION

The purpose of this Statistical Analysis Plan (SAP) is to provide a description of the statistical methods to be implemented for the analysis of data from the study with protocol number AVM-003-HC. The SAP will be finalized prior to the interim analysis for futility. Any deviations from the SAP after database lock will be documented in the final Clinical Study Report (CSR).

2 STUDY OVERVIEW

2.1 Study Objectives

2.1.1 Primary Objective

The primary objective is to compare the time to resolution of macroscopic hematuria in recipients of posoleucel (PSL, ALVR105; formerly ALVR-105, Viralym-M) to that in recipients of placebo.

2.1.2 Secondary Objectives

The key secondary objective is to compare the time to resolution of bladder pain as measured by clinical outcome assessments (COAs) in recipients of PSL to that in recipients of placebo.

Other secondary objectives include comparisons of the following in recipients of PSL and recipients of placebo:

- To assess number of days in the hospital (for any reason including hemorrhagic cystitis [HC]) over the 24-week study period.
- To assess the incidence of acute graft versus host disease (GVHD) and cytokine release syndrome (CRS) over the 24-week study period.
- To assess time to resolution of viremia for each target virus over the 24-week study period (only for participants with detectable viremia at randomization).
- To assess average daily bladder pain over the 24-week study period.
- To assess time to global impression of hemorrhagic cystitis severity of none or mild.

2.1.3 Exploratory Objectives

The exploratory objectives include comparisons of the following in recipients of PSL and recipients of placebo as measured over the 24-week study period:

- Cumulative days and time to discontinuation of supportive bladder care for HC, specifically continuous bladder irrigation and/or nephrostomy tubes.
- Summary of HC-associated signs and symptoms other than bladder pain.
- Incidence and time to recurrence of HC.
- Incidence and time to recurrence of bladder pain.
- Requiring red blood cell (RBC) and/or platelet transfusions and the number of required RBC and/or platelet transfusions (measured in transfusion units/participant).
- Change in renal function as assessed by estimated glomerular filtration rate (eGFR). For participants requiring dialysis, number of days on dialysis will be captured.

- Time to resolution of BK viruria. Resolution of viruria will be defined by the lower limits of quantitation of the assay used.
- Viremia and viruria with each target virus (ie, BKV, AdV, CMV, HHV-6, JCV, and/or EBV) over time.
- Length of use of any pain medication(s) (IV, oral, or other), including antispasmodics anticholinergics, and beta-3-agonists, used for control of lower abdominal/bladder pain.
- Use of immunosuppressive agents, by specific agent during the study.
- Number of hospitalizations, number of intensive care unit (ICU) stays, and number of days of ICU care for any reason.
- Use of antiviral therapies other than cidofovir with potential activity against at least one target virus by specific agent during the study.
- Overall survival, defined as time to death (from any cause) from the time of randomization in days.
- Incidence of relapse or progression of primary malignancy.
- Overall quality of life as measured by EuroQol 5 Dimensions (EQ-5D) questionnaires.
- Global impression of hemorrhagic cystitis change.

2.2 Study Design

2.2.1 Overview

This is a Phase 3, multicenter, double-blind, placebo-controlled trial to assess the efficacy and safety of PSL compared to placebo for the treatment of participants with virus-associated HC following allogeneic hematopoietic cell transplant (HCT).

The study hypothesis is that the administration of PSL to participants with virus-associated HC will demonstrate superiority for the time to resolution of HC (as measured by resolution of macroscopic hematuria) compared to participants treated with placebo. The primary hypothesis will be tested in participants with BKV viruria to demonstrate superiority over placebo in this population (BK Intent-to-Treat [ITT] Population). The analysis will also be conducted in all participants with any virus-associated HC (BKV, AdV, CMV, HHV-6, JCV, and/or EBV) in order to evaluate efficacy in this broader population (overall ITT Population).

Participants who meet all of the inclusion criteria and none of the exclusion criteria will be randomized in a sequence in the sequential infusions of PSL cells or placebo and will be monitored for resolution of macroscopic hematuria as defined by the primary endpoint. Randomization will be stratified by

In the dosing strategy being evaluated in this study, all participants will receive infusions of either PSL or placebo separated by (± 3) days.

The specific PSL cell line for infusion will be selected using an electronic-based software system (CytoMatch)

. Cryopreservation media

(without cells) will serve as the placebo and will be identical in volume and appearance to PSL.

AlloVir, Inc.	Statistical Analysis Plan
AVM-003-HC	V1.0 14 November 2023

All randomized participants will undergo regular visual inspections of freshly collected urine samples for: 1) the presence or absence of visible blood, and 2) the presence or absence of blood clots. The schedule of assessments will be determined by the treatment location (inpatient vs. outpatient), time on study (through the end of Week 6 [Day 42] vs. after Week 6), and status of macroscopic hematuria (unresolved vs. resolved), as shown in Table 1. Each time that a participant undergoes a urine visual assessment for Bedi grading, the same sample should be sent for urinalysis.

Treatment	Maaraaania	Time on Study		
Location	Hematuria [1]	Through the End of Week 6 (Day 42)	After Week 6	
Inpatient	Unresolved	Bedi assessment with U/A 3 × per week	Bedi assessment with U/A 2 × per week ≥2 days apart	
	Resolved	Bedi assessment with U/A 1 × per week	Bedi assessment with U/A 1 × per week	
Outpatient	Unresolved	Hemostick daily; Bedi assessment with U/A 1 × per week	Hemostick 2 × per week ≥2 days apart; Bedi assessment with U/A 1× per week	
	Resolved	Hemostick 1× per week; Bedi assessment with U/A 1 × per week	Hemostick 1 × per week; Bedi assessment with U/A at Week 12 and 24 study visits	

Table 1. Thume of visual Other Assessments with Otharysis	Table 1.	Timing of Visual	Urine Assessments	with Urinalysis
---	----------	------------------	--------------------------	-----------------

[1] Resolved macroscopic hematuria is defined as resolution to Grade 0 or 1 on the Bedi scale as assessed by an HCP on the study team on 2 consecutive visual urine assessments ≥2 days apart without continuous bladder irrigation or nephrostomy tubes that are uncapped. However, if a participant has nephrostomy tubes that are capped, Bedi assessments may be performed on urine voided through the urethra or a bladder catheter (eg, Foley or suprapubic catheter), including for the purpose of assessing for resolution. Abbreviations: HCP = healthcare provider; U/A = urinalysis

In support of the key secondary objective, bladder pain will be assessed using age-appropriate COAs.

Participants will also have urine and blood samples sent at prespecified intervals during the study to monitor viral loads of all the viruses targeted by PSL (BKV, AdV, CMV, HHV-6, JCV, and EBV). For participants who develop symptoms and/or signs of possible virus-associated gastrointestinal disease, and whose treating physician determines that laboratory evaluation of stool specimens for diagnostic and/or monitoring reasons is clinically indicated, stool samples for AdV and CMV viral load determination should, when possible, be sent to the central laboratory. Similarly, for participants who develop symptoms and/or signs of possible virus-associated neurological disease, and whose treating physician determines that laboratory evaluation of cerebrospinal fluid (CSF) for diagnostic and/or monitoring reasons is clinically indicated, CSF samples for CMV, HHV-6, and JCV viral load determination should, when possible, be sent to the central laboratory. Be sent to the central laboratory evaluation of cerebrospinal fluid (CSF) for diagnostic and/or monitoring reasons is clinically indicated, csF samples for CMV, HHV-6, and JCV viral load determination should, when possible, be sent to the central laboratory.

Safety assessments including, but not limited to chemistries, complete blood counts with differentials, and physical examinations will be performed. Adverse events will be assessed.

As GVHD is a theoretical safety concern, the incidence and severity of GVHD will be monitored during the study. No participants will be permitted to receive a second infusion of PSL or placebo if they develop worsening of GVHD at the proposed time of infusion of the second dose.

Analgesic use will be collected by the study staff and a pain medication log within the electronic patient-reported outcome (ePRO) system will be completed by outpatients.

Participants will be followed on the study for 24 weeks after the participant's first infusion with study treatment.

An independent Data and Safety Monitoring Board will be convened for this study to routinely monitor participant safety and evaluate a prespecified interim analysis for the purpose of potentially stopping the study early for futility.

A summary of the study design is shown in Figure 1.

Figure 1. Summary of Study Design

R = Randomization (on Day 1)

See section 3.1.1 (Analysis Day) for an explanation of the differences in definitions of day of the first dose and randomization between the SAP and the protocol.

2.2.2 Study Drug

Posoleucel is a third-party, donor-derived, "off-the-shelf," virus-specific T cell (VST) product with specificity for BKV, AdV, CMV, HHV-6, and EBV (with additional cross-reactive specificity for JCV due to the substantial homology between BKV and JCV) that is cryopreserved and available for immediate use. For more information, see the current IB.

2.2.3 Sample Size Determination

Approximately 125 participants will be randomized to achieve 105 participants in the BK ITT Population (the primary efficacy analysis population), assuming 85% of randomized participants will be included in the BK ITT Population. Enrollment in the study will continue until there are 105 participants in the BK ITT Population. Participants will be randomized in a ratio to receive PSL or placebo. Assuming the median times to resolution for the placebo arm and the PSL arm are, respectively, 12 weeks and 6 weeks; time to resolution follows an exponential distribution; 24 weeks of follow-up; use of a log-rank test; one interim analysis for futility; Type I error rate at the one-sided 0.025 level; 20% of participants are censored for losses to follow-up or dropout by 24 weeks; time to censoring follows an exponential distribution and is equivalent in the two arms, the study will have 86.4% power.

2.3 Study Endpoints

2.3.1 Primary Efficacy Endpoint

The primary endpoint is the time to resolution of macroscopic hematuria in participants with documented BK viruria. A supplementary analysis will evaluate the time to resolution of macroscopic hematuria in participants with any virus-associated HC. Resolution of macroscopic hematuria is defined as resolution to Grade 0 or 1 on the Bedi scale as assessed by the Investigator on 2 consecutive visual urine assessments with urinalysis ≥2 days apart without continuous bladder irrigation or nephrostomy tubes that are uncapped. However, if a participant has nephrostomy tubes that are capped, Bedi assessments may be performed on urine voided through the urethra or a bladder catheter (eg, Foley or suprapubic catheter), including for the purpose of assessing for resolution.

A healthcare provider (HCP) on the study team (including a home health provider) may perform the visual urine assessment, but it is the Investigator's responsibility to determine the Bedi grade. Grade 0 requires no detectable blood by urinalysis; Grade 1 hematuria requires confirmation of resolution by urinalysis results of ≤100 RBCs/high power field (HPF).

Participants will be followed for the primary endpoint for a maximum of 24 weeks from the date of randomization.

Definitive therapies to stop bladder bleeding, including cystectomy, bladder vessel embolization, cauterization, fulguration, or formalin instillation are permitted, but will be considered treatment failures for the primary endpoint of time to resolution of macroscopic hematuria. Participants with ongoing continuous bladder irrigation should be evaluated daily by the Investigator for the ability to discontinue this supportive measure.

Participants who are receiving continuous bladder irrigation or who have nephrostomy tubes that are uncapped at randomization will be considered to have Bedi Grade 3 hematuria at randomization. For participants undergoing continuous bladder irrigation, the primary endpoint (ie, time to resolution of macroscopic hematuria) will be measured once participants discontinue continuous bladder irrigation. Bedi grading will not be performed on days on which the participant is receiving continuous bladder irrigation. Discontinuation of continuous bladder irrigation will be based upon the participant's clinical condition and the treating physician's medical judgement.

If, following resolution of macroscopic hematuria, recurrence is observed, a Bedi assessment with urinalysis will be obtained and the date of recurrence observed by the Investigator will be recorded. Urine obtained at the time of recurrence will also be sent for BKV, AdV, CMV, HHV-6, JCV, and EBV viral load determination and banking of viral deoxyribonucleic acid for potential genotyping. A second Bedi assessment with urinalysis will be repeated ≥2 days after the date of recurrence observed by the Investigator. Recurrence is defined as 2 consecutive Bedi grades ≥2 with macroscopic hematuria (visibly bloody urine) that are at least 2 days apart. Participants with recurrence will then undergo visual assessment of urine and urinalysis as indicated in Table 1 for those with unresolved hematuria and according to the participant's treatment location and time on study. Following resolution of recurrent hematuria, follow Table 1 for those with resolved hematuria.

2.3.2 Secondary Efficacy Endpoints

The key secondary endpoint is the time to resolution of bladder pain as measured by ageappropriate COAs. Resolution of pain is defined as participants achieving a score on the relevant COA that does not exceed "mild pain," confirmed with 2 consecutive scores, without use of prescription pain medications (not PRN or "as needed") or the use of supportive bladder care, specifically continuous bladder irrigation and nephrostomy tubes.

Mild bladder pain is defined as:

- In participants ≥12 years of age: a score ≤3 on the worst daily pain question from the Bladder Pain/Interstitial Cystitis Symptom Diary (BPIC SD).
- In participants 3 to 11 years of age: a score ≤2 on the Wong-Baker FACES® Pain Rating Scale.

The analysis will include all participants whose pain scores exceed "mild pain" at randomization, or who are receiving prescription pain medications (not PRN or "as needed") or supportive bladder care at randomization. Use of prescription pain medications (not PRN or "as needed") or supportive bladder care will be considered equivalent to pain that exceeds "mild pain." If the pain scores at randomization are missing, the screening pain scores will be used. Otherwise, the participant will not be included in the analysis.

This endpoint will not be assessed in participants <3 years of age as there is no COA that has been validated for this purpose. Instead, data regarding pain behaviors will be collected in this age group using the Patient-Reported Outcomes Measurement Information System® (PROMIS) Parent Proxy Pain Behavior Short Form.

Additional secondary efficacy endpoints include the following:

- Number of days in the hospital (for any reason including, but not limited to, HC) over the 24-week study period.
- Time to resolution of viremia for each target virus (ie, BKV, AdV, CMV, HHV-6, JCV, and/or EBV) over the 24-week study period (only for participants with detectable viremia at randomization). Evaluation of this endpoint will be based on viremia quantitation performed at the central laboratory. Resolution of viremia will be defined by the lower limits of quantitation (LLOQ) of the assays used (BKV, AdV, CMV, HHV-6, JCV are measured in the plasma, EBV is measured in peripheral blood mononuclear cells).
- Average daily bladder pain over the 24-week study period, without use of prescription pain medications (not PRN or "as needed") or supportive bladder care.
- Time to global impression of hemorrhagic cystitis severity of none or mild, confirmed with 2 consecutive scores, without use of prescription pain medications (not PRN or "as needed") or supportive bladder care.

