The key secondary endpoint is the time to resolution of bladder pain as measured by age-appropriate COAs. Resolution of pain is defined as participants achieving a score on the relevant COA that does not exceed "mild pain" (ie, scores of 3 or below on the Bladder Pain/Interstitial Cystitis Symptom Diary [BPIC SD], 0 to 10 NRS capturing participants' worst daily pain among adolescents ≥12 years of age and adults and a parallel assessment for children 3 to 11 years of age as a score that does not exceed 2 on the Wong-Baker FACES® Pain Rating Scale), without use of prescription pain medications or the use of supportive bladder care.

This endpoint will not be assessed in participants <3 years of age.

Other Secondary Efficacy Endpoints

Additional secondary efficacy endpoints include the following:

- Number of days in the hospital (for any reason including, but not limited to, HC) over the 24-week study period.
- Time to resolution of viremia for all target viruses (ie, BKV, AdV, CMV, HHV-6, JCV, and/or EBV) over the 24-week study period (only for participants with detectable viremia at baseline). Evaluation of this endpoint will be based on viremia quantitation performed at the central laboratory. Resolution of viremia will be defined by the lower limits of detection of the assays used.
- Average daily bladder pain (including lower abdominal pain, bladder-related pressure, and/or spasm pain or dysuria) over the initial 6 weeks following randomization.

SAFETY VARIABLES:

The safety endpoints include the following:

- Incidence and severity of acute GVHD (secondary endpoint)
- Incidence and severity of chronic GVHD (exploratory endpoint)
- Incidence and severity of CRS (secondary endpoint)

Safety assessments will also include adverse events, vital signs, 12-lead electrocardiograms (ECGs), physical examination findings, and clinical laboratory assessments.

STATISTICAL ANALYSES:

Summary statistics will be presented by treatment group. Unless otherwise stated, continuous variables will be summarized using the number of non-missing observations, arithmetic mean, standard deviation, median, minimum, and maximum values as descriptive statistics. Categorical variables will be summarized using the frequency count and the percentage of participants in each category as descriptive statistics.

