2.2 Secondary Objectives

The key secondary objective is to compare the time to resolution of bladder pain as measured by Clinical Outcome Assessments (COAs) in recipients of PSL to that in recipients of placebo.

Other secondary objectives include comparisons of the following in recipients of PSL and recipients of placebo:

- To assess number of days in the hospital (for any reason including HC) over the 24-week study period.
- To assess the incidence and severity of acute GVHD and cytokine release syndrome (CRS) over the 24-week study period.
- To assess time to resolution of viremia for all target viruses over the 24-week study period (only for participants with detectable viremia at baseline).
- To assess average daily bladder pain (11-point numeric rating scale [NRS]) over the 6-week period from randomization.

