7 EFFICACY ASSESSMENTS

The primary endpoint is the time to resolution of macroscopic hematuria in participants with documented BK viruria. Resolution of macroscopic hematuria is defined as resolution to Grade 0 or 1 on the Bedi scale⁴⁷ as assessed by an HCP on the study team on 2 consecutive visual urine assessments ≥ 2 days apart without continuous bladder irrigation or nephrostomy tubes; Grade 1 hematuria requires confirmation of resolution by urinalysis results of ≤ 100 RBCs/high power field (HPF). If a participant has nephrostomy tubes that are capped, Bedi assessments may be performed, including for the purpose of assessing for resolution. Details of the macroscopic hematuria assessment are provided in Section 7.1.

The key secondary endpoint is the time to resolution of bladder pain as measured by age-appropriate COAs. Resolution of bladder pain is defined as participants achieving a score on the relevant COA that does not exceed "mild pain" without use of prescription pain medications or the use of supportive bladder care.

Mild bladder pain is defined as:

- In participants ≥12 years of age: a score ≤3 on the worst daily pain question from the Bladder Pain/Interstitial Cystitis Symptom Diary (BPIC SD).
- In participants 3 to 11 years of age: a score ≤2 on the Wong-Baker FACES® Pain Rating Scale.

This endpoint will not be assessed in participants <3 years of age as there is no COA that has been validated for this purpose. Instead, data regarding pain behaviors will be collected in this age group using the Patient-Reported Outcomes Measurement Information System® (PROMIS) Parent Proxy Pain Behavior Short Form.

Additional secondary efficacy endpoints include the following:

- Number of days in the hospital (for any reason including, but not limited to, HC) over the 24-week study period.
- Time to resolution of viremia for all target viruses (ie, BKV, AdV, CMV, HHV-6, JCV, and/or EBV) over the 24-week study period (only for participants with detectable viremia at baseline).
 Evaluation of this endpoint will be based on viremia quantitation performed at the central laboratory. Resolution of viremia will be defined by the lower limits of detection of the assays used.
- Average daily bladder pain (including lower abdominal pain, bladder-related pressure, and/or spasm pain or dysuria) over the initial 6 weeks following randomization.

The exploratory efficacy endpoints include the following:

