9.2.1.3 Other Efficacy Analysis

If the result of the key secondary efficacy analyses based on the BK ITT and overall ITT Populations are both statistically significant, a formal hypothesis test will be conducted sequentially of the first other secondary endpoint, number of days in the hospital, based on the BK ITT Population. The analysis will be performed using a linear regression model with terms for treatment and the stratification factors at randomization. This secondary endpoint will be tested at the one-sided 0.025 alpha level. Sensitivity analyses will be performed based on the BK mITT and BK PP Populations.

If the result of the analysis based on the BK ITT Population is statistically significant, a formal hypothesis test of this endpoint will be conducted based on the overall ITT Population using a 0.025 alpha level. A sensitivity analysis will be conducted using the mITT Population.

The sequential testing described above will control the overall Type I error for these endpoints at the one-sided 0.025 level.

Other continuous and categorical efficacy endpoints (including secondary and exploratory endpoints not selected for hierarchical testing above) will be summarized descriptively by treatment groups using appropriate populations. Categorical endpoints will be summarized using the number and percentage of participants within each category.

Time-to-event endpoints will be summarized using Kaplan-Meier estimates. In addition, the hazard ratio along with the 95% confidence intervals for the true hazard ratio will be calculated using a Cox proportional hazards model with treatment, stratification factors at randomization, and other potentially confounding factors.

There is no adjustment for multiplicity in the analyses of these other efficacy endpoints.

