Time to resolution of viremia for each target virus (ie, BKV, AdV, CMV, HHV-6, JCV, and/or EBV) over the 24-week study period (only for participants with detectable viremia at randomization) will be analyzed using Kaplan-Meier estimates, and treatment effect will be compared using stratified log-rank test and hazard ratio with stratified Cox proportional model. Evaluation of this endpoint will be based on viremia quantitation performed at the central laboratory. Resolution of viremia will be defined by the lower limits of quantitation (LLOQ) of the assays used (BKV, AdV, CMV, HHV-6, JCV are measured in the plasma, EBV is measured in peripheral blood mononuclear cells). Only participants who had viremia at randomization for each target virus will be included in the analysis.

Average daily bladder pain (ie, the participant's average bladder pain over the previous 24 hours) will be recorded daily for the first 6 weeks of the study and once weekly thereafter. The average daily bladder pain will be averaged for each week for the first 6 weeks and starting at Week 7, the single average daily pain score will be recorded. The applicable weekly measures will be summarized by treatment group over the 24-week study period. Only pain assessments

without use of prescription pain medications (not PRN or "as needed") or supportive bladder care will be used.

Time to global impression of hemorrhagic cystitis severity of none or mild, confirmed with 2 consecutive scores, will be analyzed similar to the key secondary endpoint. The analysis will include all the participants who exceed "mild" at randomization. If the scores at randomization are missing, a prior score will be used if available. Otherwise, the participant will not be included in the analysis. Time to resolution will be calculated from the date of randomization to the date of the first time reaching the global impression of hemorrhagic cystitis severity of non or mild, without use of prescription pain medications (not PRN or "as needed") or supportive bladder care. Participants not observed to achieve the threshold will be considered censored at their last follow up.

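### The SAP turns the protocol's 6-week average bladder pain endpoint into 24 weeks of off-analgesic weekly summaries, gives no reason, and produces no 6-week result

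*SAP*

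**What the plan says.** **Protocol.** The secondary objective (Synopsis and 2.2) is "To assess average daily bladder pain (11-point numeric rating scale [NRS]) over the 6-week period from randomization". The matching endpoint (Synopsis and Section 7) is "Average daily bladder pain (including lower abdominal pain, bladder-related pressure, and/or spasm pain or dysuria) over the initial 6 weeks following randomization". Neither statement makes a score's use depend on analgesics or bladder care. The objectives are introduced as comparisons: "Other secondary objectives include comparisons of the following in recipients of PSL and recipients of placebo". For secondary endpoints outside the testing hierarchy, however, Protocol 9.2.1.3 plans only that they "will be summarized descriptively by treatment groups using appropriate populations".

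**SAP.** The objective in 2.1.2 reads "To assess average daily bladder pain over the 24-week study period". The endpoint in 2.3.2 is "Average daily bladder pain over the 24-week study period", limited to time off prescription pain medication other than as-needed use and off supportive bladder care. Section 3.4.3 averages the daily scores within each of Weeks 1 to 6, takes the single weekly score from Week 7, and adds: "The applicable weekly measures will be summarized by treatment group over the 24-week study period". It repeats that scores recorded on those treatments are not used. The lead-in to the same list in 3.4.3 says the listed endpoints are analyzed in the BK ITT Population at the one-sided 0.025 level.

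**The concern.** A named secondary endpoint changes in two respects between protocol and SAP, and neither change is flagged.

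- **The window.** Six weeks is the period in which pain is recorded daily (Protocol 7.2.1), so a mean of daily pain is well defined there. After Week 6 there is one score per week.
- **The scores that count.** Whether a participant is on a scheduled analgesic or bladder irrigation in a given week is decided after randomization and may itself depend on treatment. Dropping those scores means each weekly summary compares arms on whoever happens to be off such care that week, not on the randomized groups.

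If the SAP is followed as written, the study report will contain no estimate of the quantity that the protocol named, and the early-week summaries cannot be combined to recover it.

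**Working it through.** No stated figure is in dispute, so there is nothing to reproduce. The check sets the texts side by side and then uses assumed scores to show that the two definitions give different quantities.

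**1. The texts compared**

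| Element | Protocol (Synopsis, 2.2, 7, 9.2.1.3) | SAP (2.1.2, 2.3.2, 3.4.3) |
|---|---|---|
| Window | 6 weeks from randomization | 24 weeks |
| Scores used | No restriction stated | Only off scheduled prescription analgesics and supportive bladder care |
| Unit reported | Average over the window | One value per week |
| Method | Descriptive by arm | Weekly summary by arm; the list's lead-in sets a one-sided 0.025 level, but no test, model or estimate is named |
| Reason for change | n/a | None given |

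The SAP does point out its different day numbering (3.1.2), so it flags at least one departure from the protocol, but not this one.

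**2. The window.** Weeks 1 to 6 give 6 of 24 weekly values: 6/24 = 25%. The other 18 (75%) fall outside the protocol's period and are single scores, not means of up to seven. Assume an arm difference of 1 to 2 NRS points confined to Weeks 1 to 6. Averaged equally over 24 weekly values it becomes 1 × 6/24 = 0.25 to 2 × 6/24 = 0.50. The SAP does not plan that average. The figures show only how far a 24-week reading dilutes an early effect.

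**3. The restriction.** Assume a participant who scores 8 in Weeks 1 to 3 on a scheduled analgesic, 2 in Weeks 4 to 6 off it, and 1 in Weeks 7 to 24.

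- 6-week mean of all scores: (3 × 8 + 3 × 2)/6 = 30/6 = 5.0.
- Scores usable under the SAP, Weeks 1 to 6: (3 × 2)/3 = 2.0.
- Scores usable under the SAP, Weeks 1 to 24: (3 × 2 + 18 × 1)/21 = 24/21 = 1.14.

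A second participant with the same pain but no scheduled analgesic has 5.0 over Weeks 1 to 6 under either rule. On the usable scores the two differ by 5.0 − 2.0 = 3.0 points, although their pain is identical. In the SAP's weekly display, the first participant is simply absent from Weeks 1 to 3.

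**4. Can the protocol's quantity be rebuilt from the SAP's output?** No. The excluded scores are missing from the weekly values, and arm-level weekly summaries carry neither each participant's 6-week mean nor its standard error.

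**The case against.** **The protocol planned no test here either.** This stands. A reader might infer that the SAP removed a comparison. It did not: Protocol 9.2.1.3 and the Synopsis both limit such endpoints to descriptive summaries. A model with a confidence interval would therefore be an addition. What remains is that both documents call the objective a comparison, and SAP 3.4.3 sets a one-sided level for its list without giving this endpoint a method.

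**The protocol's period is still reported.** Largely true. Values for each of Weeks 1 to 6 will appear by arm, so it would be wrong to infer that the early data disappear. They appear only for participants off the listed treatments, and without a 6-week summary.

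**Average pain is a diary item.** The symptom diary has separate average-pain and worst-pain questions (Protocol 7.2.1), and the protocol never spells out one mean per participant over 42 days. This is fair, and the SAP should settle it. On either reading the window is 6 weeks and the scores are unrestricted.

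**Scores under analgesia are masked.** This is a sensible reason for caution, and the key secondary endpoint also requires freedom from prescription pain medication. There, however, a participant on such medication counts as still in pain (SAP 2.3.2). In a weekly mean the same exclusion removes the participant altogether.

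**Later pain data are of interest.** Yes. The diary runs weekly to Week 24, and Protocol 2.3 lists pain level at Weeks 2, 4, 6, 8 and 12 as exploratory. That supports adding 24-week summaries, not replacing the 6-week endpoint.

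**Conclusion.** The point holds as an unexplained replacement of a named secondary endpoint. It should be corrected, but it does not threaten the trial's main conclusions: average pain lies outside the alpha-controlled sequence, so type I error, power, and the primary and key secondary analyses are unaffected.

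The size in pain units cannot be stated. The documents give no mean, SD or expected effect for pain and no rate of analgesic use by arm, so even the direction of any selection effect is unknown. The 5.0 against 2.0 comparison rests on assumed scores.

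A reader might try to size the change from the design's hematuria medians of 12 and 6 weeks. The average over weeks of 2^(−t/12) − 2^(−t/6) is 0.140 for Weeks 1 to 6 and 0.207 for Weeks 1 to 24. The arithmetic is right, but those are shares with unresolved hematuria, not pain scores, and they say nothing about this endpoint.

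The verdict assumes that no later protocol amendment moved the window. None is among the documents, and the SAP cites none for this endpoint.

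**What to change.** In SAP 2.1.2, 2.3.2 and 3.4.3:

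- **Restore the 6-week endpoint.** Define it as each participant's mean of the daily average-pain NRS scores over the daily-diary period, through Day 42. Use every recorded score regardless of analgesic or supportive-care use.
- **State who contributes.** Participants aged 12 or older, who complete the diary's average-pain item. Children aged 3 to 11 complete the FACES scale and those under 3 have a caregiver form (Protocol 7.2), so their scores cannot enter the same mean.
- **Name the estimate.** Report the between-arm difference with 95% CI from a linear model with baseline score and the stratification factors, without multiplicity adjustment. Reconcile this with the one-sided 0.025 lead-in in 3.4.3, which currently has no method attached for this endpoint.
- **Keep the 24-week off-medication weekly summaries** as additional, labeled as restricted to a subset defined after randomization.
- **Document the departure from the protocol**, with its reason.

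The cost is SAP wording and one simple model on data already collected. The limitation to state alongside it is that a mean of all scores describes pain under whatever analgesia was given, so analgesic use should be read next to it.
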